- added a summary for treatment disposition
- added patient characteristic reporting for Visit 1 of Study AMAH in addition to the baseline of originating studies for measures that may change over time
- included definition and summary for prior medications
- updated Table AMAH.5.3 and Table AMAH.5.4 with additional details, including:
 - clarification of definitions of missing components
 - addition of sPGA(0)
 - addition of PASI 75
 - addition of PSS signs score
 - addition of PSSI score = 0
 - addition of NAPSI score = 0
 - addition of PPASI 50, PPASI 75, and PPASI 100
 - addition of DLQI (0,1) and DLQI total score ≥ 5 improvement from baseline
- added summaries to characterize patients that increase dosing
- added the analysis section for Japan submission and the Appendix of Analysis Plan for the Japan Addendum
- updated guidelines on interim database locks
- made other minor typographical corrections and clarifications not affecting content

4. Study Objectives

Table AMAH.4.1 shows the protocol defined objectives and endpoints of the study. The estimand (ICH E9 R1) associated with each endpoint/analysis is documented in the following places:

- The population and cohort of interest is described in the protocol inclusion/exclusion criteria and in this document in Section 6.1.1.
- The endpoints/variables are listed in Table AMAH.4.1, Table AMAH.6.3 and Table AMAH.6.4.
- The handling of intercurrent events is summarized in Sections 6.3.
- Population level summary measures are described in Section 6.9 and Table AMAH.6.4.

Table AMAH.4.1. Protocol Defined Objectives and Endpoints

Objectives	Endpoints

Primary
 
To evaluate the long-term maintenance of efficacy of mirikizumab in patients with moderate-to-severe plaque psoriasis
	
Over the duration of the study:
 
 • Proportion of patients with an sPGA (0,1) among those who entered Study AMAH with sPGA (0,1) • Proportion of patients who maintained a $\geq 90\%$ improvement in PASI (PASI 90) among those who entered Study AMAH with a PASI 90 response

Secondary
 
To evaluate the long-term efficacy and patient reported outcomes with mirikizumab treatment in patients with moderate-to-severe plaque psoriasis
	
Over the duration of the study:
 
 • Proportion of patients achieving sPGA (0,1) • Proportion of patients achieving PASI 90 • Proportion of patients achieving a 100% improvement in PASI (PASI 100) • Proportion of patients with a Psoriasis Symptoms Scale (PSS) symptom score of 0 (free of itch, pain, stinging, and burning) in those with a PSS symptoms score ≥ 1 at baseline. • Proportion of patients achieving a Dermatology Life Quality Index (DLQI) total score of (0,1) with at least a 5-point improvement (reduction) from baseline in patients with a baseline DLQI total score $\geq 5^*$ • Change in Palmoplantar Psoriasis Severity Index (PPASI) total score in patients with palmoplantar involvement at baseline* • Change in Psoriasis Scalp Severity Index (PSSI) total score in patients with scalp involvement at baseline* • Change in Nail Psoriasis Severity Index (NAPSI) total score in patients with fingernail involvement at baseline*

Objectives	Endpoints

Exploratory
 
To evaluate the potential development of anti-mirikizumab antibodies and their potential relationship with efficacy, TEAEs, and mirikizumab exposure
	
Over the course of the 208 week study, by treatment-emergent anti-drug antibody (TE-ADA) status and by neutralizing anti-drug antibody (NAb) status:
 
 • Relationship between ADA and efficacy (sPGA and PASI) • Relationship between ADA and TEAEs • Relationship between TE-ADA and mirikizumab pharmacokinetics

Abbreviations: ADA= antidrug antibodies; DLQI = Dermatology Life Quality Index; Nab = neutralizing anti-drug antibody; NAPSI = Nail Psoriasis Severity Index; PASI = Psoriasis Area and Severity Index; PPASI = Palmoplantar Psoriasis Severity Index; PSS = Psoriasis Symptoms Scale; PSSI = Psoriasis Scalp Severity Index; sPGA = static Physician’s Global Assessment; TE-ADA = treatment-emergent anti-drug antibody; TEAEs = treatment-emergent adverse events.

* Secondary objectives have been updated to align with a protocol amendment (a) to Study AMAK and protocol amendment (b) to Study AMAJ. Since Study AMAH has not had another protocol amendment, changes have been reflected in this SAP but differ from those listed in the Study AMAH protocol amendment (a).

5. Study Design

Study AMAH is a long-term study in which patients completing one of the originator studies (AMAF, AMAJ, AMAK, or AMBK) will receive 250 mg or 125 mg mirikizumab every 8 weeks (Q8W), administered subcutaneous (SC), for an extended period of time (approximately 4 years or until commercial availability of mirikizumab) and then enter a 12-week Post-Treatment Follow-Up period.

At the time of SAP Version 2, Study AMBK had not begun. In the event that Study AMBK begins while Study AMAH is ongoing, participants from Study AMBK may be allowed to participate in Study AMAH, and this SAP will be amended accordingly.

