
Secondary
 
 To evaluate the long-term efficacy and patient reported outcomes with mirikizumab treatment in patients with moderate-to-severe plaque psoriasis 	
Over the duration of the study:
 
 Proportion of patients achieving sPGA (0,1) Proportion of patients achieving PASI 90 Proportion of patients achieving a 100% improvement in PASI (PASI 100) Proportion of patients with a PSS symptom score of 0 (free of itch, pain, stinging, and burning) in those with a PSS symptoms score ≥ 1 at baseline. Proportion of patients achieving Dermatology Life Quality Index (DLQI) score of 0,1 with baseline score > 1 Percent change in Palmoplantar Psoriasis Severity Index (PPASI) total score in patients with palmoplantar involvement at baseline Percent change in Psoriasis Scalp Severity Index (PSSI) total score in patients with scalp involvement at baseline Percent change in Nail Psoriasis Severity Index (NAPSI) total score in patients with fingernail involvement at baseline

Exploratory
 
To evaluate the potential development of anti-mirikizumab antibodies and their potential relationship with efficacy, TEAEs, and mirikizumab exposure
	
Over the course of the 208 week study, by treatment-emergent anti-drug antibody (TE-ADA) status and by neutralizing anti-drug antibody (NAb) status:
 
 • Relationship between ADA and efficacy (sPGA and PASI) • Relationship between ADA and TEAEs • Relationship between TE-ADA and mirikizumab pharmacokinetics
---	---

Abbreviations: ADA= antidrug antibodies; DLQI = Dermatology Life Quality Index; Nab = neutralizing anti-drug antibody; NAPSI = Nail Psoriasis Severity Index; PASI = Psoriasis Area and Severity Index; PPASI = Palmoplantar Psoriasis Severity Index; PSS = Psoriasis Symptoms Scale; PSSI = Psoriasis Scalp Severity Index; sPGA = static Physician’s Global Assessment; TE-ADA = treatment-emergent anti-drug antibody; TEAEs = treatment-emergent adverse events.

5. Study Design

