6.1. General Considerations

Statistical analysis of this study will be the responsibility of Eli Lilly and Company (hereafter, Lilly) or its designee. The latest version of the Medical Dictionary for Regulatory Activities (MedDRA[®]) will be used.

Analyses and summaries from assessment of endpoints described in [Table AMAH.4.1](#) of this Statistical Analysis Plan are planned to be included in the clinical study report (CSR). Analyses and summaries for key safety data are also planned to be included in the CSR. Results from additional efficacy analysis pre-defined below and other safety analyses may also be provided in the CSR, as deemed appropriate. Any analysis or summary not included in the CSR will be available upon request.

Any change to the data analysis methods described in the protocol will require a protocol amendment ONLY if it changes a principal feature of the protocol. Any other change to the data analysis methods described in the protocol and the justification for making the change will be described in the CSR.

Additional exploratory analyses of the data may be conducted, as deemed appropriate. Some of these additional supplementary analyses will be prespecified in a separate supplemental SAP.

Some of the analyses described in this document will be incorporated into interactive display tools instead of or in addition to static displays.

The Schedule of Activities outlined in the protocol specifies the allowable windows for assessments. Assessments performed outside these windows will not be excluded from any analysis.

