sPGA	sPGA (0,1) (Primary)	Descriptive analysis with Observed, NRI, mNRI and Multiple Imputation	ITT - patients who entered Study AMAH with sPGA (0,1)	All visits in corresponding periods
	sPGA (0); sPGA (0,1) (Secondary)	Descriptive analysis with Observed, NRI, mNRI and Multiple Imputation	ITT	All visits in corresponding periods
PSS	PSS symptoms score of 0;	Descriptive analysis with Observed, NRI, mNRI and Multiple Imputation	ITT – patients with a PSS symptoms score ≥ 1 at Baseline	All visits in corresponding periods
	PSS signs score of 0;	Descriptive analysis with Observed, NRI, mNRI and Multiple Imputation	ITT – patients with a PSS signs score ≥ 1 at Baseline	All visits in corresponding periods
PSSI	PSSI change from baseline	Descriptive analysis with Observed and Multiple Imputation	ITT - patients with Scalp Involvement at Baseline	All visits in corresponding periods
	PSSI = 0	Descriptive analysis with Observed, NRI, mNRI and Multiple Imputation	ITT – patients with Scalp Involvement at Baseline	All visits in corresponding periods
PPASI	PPASI change from baseline	Descriptive analysis with Observed and Multiple Imputation	ITT - patients with Palmoplantar Involvement at Baseline	All visits in corresponding periods

Measure	Variable	Analysis Method (Section 6.1.3)	Population (Section 6.1.1)	Time Point
	PPASI 50; PPASI 75; PPASI 100	Descriptive analysis with Observed, NRI, mNRI and Multiple Imputation	ITT – patients with Palmoplantar Involvement at Baseline	All visits in corresponding periods
NAPSI	NAPSI change from baseline	Descriptive analysis with Observed and Multiple Imputation	ITT - patients with Nail Psoriasis Involvement at Baseline	All visits in corresponding periods
	NAPSI = 0	Descriptive analysis with Observed, NRI, mNRI and Multiple Imputation	ITT – patients with Nail Psoriasis Involvement at Baseline	All visits in corresponding periods
DLQI	DLQI (0,1)	Descriptive analysis with Observed, NRI, mNRI and Multiple Imputation	ITT - patients with Baseline DLQI > 1	All visits in corresponding periods
	DLQI (0,1) and ≥5-point reduction from Baseline	Descriptive analysis with Observed, NRI, mNRI and Multiple Imputation	ITT – patients with DLQI ≥5 at Baseline	All visits in corresponding periods

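### SAP version 2 replaces percent change in PPASI, PSSI and NAPSI with absolute change without an AMAH protocol amendment, so none of these three secondary endpoints would be reported as the protocol defines it

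*SAP*

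**What the plan says.** Protocol Section 4, Table AMAH.2, lists eight secondary endpoints. Three are relative measures. The scalp entry reads "Percent change in Psoriasis Scalp Severity Index (PSSI) total score in patients with scalp involvement at baseline"; the palmoplantar (PPASI) and nail (NAPSI) entries have the same form, each a percent change among patients affected at that site.

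SAP Section 4, Table AMAH.4.1, whose title presents the list as the protocol's own, drops the word percent from all three. The scalp entry there reads "Change in Psoriasis Scalp Severity Index (PSSI) total score in patients with scalp involvement at baseline", while the palmoplantar and nail entries are altered in the same way. Each is starred. The footnote gives alignment with AMAK amendment (a) and AMAJ amendment (b) as the reason, notes that AMAH has had no further amendment, and says "changes have been reflected in this SAP but differ from those listed in the Study AMAH protocol amendment (a".

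In SAP Table AMAH.6.4 the continuous scalp analysis is "PSSI change from baseline", and the nail and palmoplantar rows match it. SAP Section 6.1 plans the study report around the endpoints in Table AMAH.4.1; other pre-defined efficacy analyses may be added as judged appropriate.

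**The concern.** The protocol in force and the SAP name different endpoint variables for the same three measures. The SAP is the document that will be programmed, and the report follows its list. A reader who starts from the protocol would look for percent change in scalp, nail and palmoplantar scores and not find it.

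The stake is faithful reporting of declared endpoints. These are descriptive secondary endpoints with no hypothesis test attached, so no error rate is affected. The title of Table AMAH.4.1 adds to the confusion, because it calls the list protocol-defined while the footnote says that it is not.

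**Working it through.** **Comparison of the documents.** The plan gives no figure to reproduce here, so the check is a comparison of protocol Table AMAH.2 with SAP Tables AMAH.4.1, 6.3 and 6.4.

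| Measure | Protocol endpoint | SAP Table 4.1 | Percent variable in Table 6.3 | Rows in Table 6.4 |
|---|---|---|---|---|
| PPASI | Percent change | Change | Yes, percent improvement with a formula | Change; PPASI 50, 75, 100 |
| PSSI | Percent change | Change | None | Change; score of 0 |
| NAPSI | Percent change | Change | None | Change; score of 0 |
| DLQI | 0 or 1, baseline above 1 | 0 or 1 with a reduction of at least 5, baseline at least 5 | Not applicable | Both versions |

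Counts for the three percent-change endpoints:

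- Changed to absolute change in Table 4.1: 3 of 3.
- No continuous percent-change row in Table 6.4: 3 of 3.
- No percent variable anywhere in the SAP: 2 of 3 (PSSI, NAPSI).
- Percent improvement derived and analysed by threshold: 1 of 3 (PPASI).

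These are 3 of the protocol's 8 secondary endpoints. DLQI is the fourth starred entry. There the SAP added the new definition and kept a row for the protocol's version.

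**Can the protocol endpoint be recovered from what is planned?** Take two invented groups of two patients each, written as baseline to follow-up. The scores lie within the ranges of both PSSI (0 to 72) and NAPSI (0 to 80).

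- Group A, 4 to 0 and 40 to 20. Mean change = (−4 − 20)/2 = −12.0. Mean percent change = (−100% − 50%)/2 = −75.0%.
- Group B, 4 to 2 and 40 to 18. Mean change = (−2 − 22)/2 = −12.0. Mean percent change = (−50% − 55%)/2 = −52.5%.

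Mean baseline is (4 + 40)/2 = 22 in both groups. Dividing mean change by mean baseline gives −12/22 = −54.5% in both, which is neither group's mean percent change. The score-of-0 row would tell these groups apart (1 of 2 against 0 of 2), but it records complete clearance only and does not say how far the other patients improved. Reporting mean absolute change with the baseline summary therefore does not yield the protocol endpoint.

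**The case against.** The strongest reply is that this was an open, reasoned and timely decision. The SAP revision history lists the update. Version 2 was approved before the first unblinding to the study team, though after unblinding to the external safety committee. AMAJ and AMAK supply 1440 + 500 = 1940 of the 205 + 1440 + 500 + 300 = 2445 planned originator patients (79%), so using their metric in the extension is sensible. All of this stands. It justifies adding absolute change; it does not require dropping percent change.

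Four stronger readings are tempting, and the documents do not support them.

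- A reader might infer that relative improvement is not analysed at all. PPASI 50, 75 and 100 are thresholds on percent improvement, and for a patient with a baseline above 0 a PSSI or NAPSI of 0 is a 100% improvement. The gap is the continuous percent-change summary.
- A reader might infer that the SAP broke its own rule, because a change "will require a protocol amendment ONLY if it changes a principal feature of the protocol". That sentence concerns data analysis methods, and neither document defines a principal feature or says that a secondary endpoint is one.
- A reader might infer a hidden or data-driven switch. The disclosure, the stated reason and the approval timing speak against it.
- A reader might infer that absolute change will mislead comparisons between cohorts. The SAP analyses efficacy separately by cohort, plans no hypothesis test, and summarises originating-study baseline PPASI, PSSI and NAPSI.

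It is also true that percent change is skewed and unstable at low baselines, so absolute change has a fair claim to be reported as well.

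**Conclusion.** The mismatch holds and is modest in size. Three of eight secondary endpoints in the governing protocol have been redefined in the SAP without an AMAH amendment, and none has a planned summary in the protocol's terms. For PSSI and NAPSI both the derivation and the analysis are missing. For PPASI only the continuous row is missing.

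This rests on protocol amendment (a) being the version in force, as the SAP footnote states. The documents cannot show whether a later amendment or the study report closes the gap. The conclusion does not depend on whether a secondary endpoint counts as a principal feature: the protocol still names these endpoints, and the plan does not analyse them as named. The reply about disclosure and timing removes any suggestion of bias but leaves the reporting gap.

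**What to change.** 1. In SAP Table AMAH.6.3, add percent change from baseline for PSSI and NAPSI, defined for patients with a baseline score above 0. State one sign convention for all three measures, since the existing PPASI variable is percent improvement, which has the opposite sign to percent change.
2. In SAP Table AMAH.6.4, add a percent-change row for PPASI, PSSI and NAPSI, with observed data and multiple imputation, reporting median and quartiles beside the mean. Percent change can be computed from the imputed scores, so no new imputation model is needed.
3. Keep the absolute-change rows, as the SAP does with the two DLQI definitions.
4. Retitle Table AMAH.4.1, or mark in it which version of each starred endpoint is the protocol's.

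The alternative is to amend the AMAH protocol so that absolute change becomes the declared endpoint.

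The cost of the SAP route is two derivations and three descriptive rows, with no new data. The downside is that percent change is skewed at low baselines, which is why the median and quartiles are asked for.

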5.1. Summary of Study Design

[figure not shown]
Patients who qualify for Study AMAH may enter directly into the study upon the last visit of a qualifying study treatment period (LVTP) of the originator study. For most patients, Week 52 of the originating study (AMAJ and AMAK) will be the LVTP and will coincide with Week 0 (Visit 1) for Study AMAH. Similar alignment will occur for other originator studies, that is, Visit 1 of Study AMAH to coincide with the LVTP in AMAF and AMBK. The qualifying study treatment periods of the originator studies are as follows:

- AMAJ, AMAK, AMAF: Blinded Maintenance Period
- AMBK: Treatment Period

Study investigator(s) will review patient data from the LVTP in the respective originating study to determine if the patient meets all inclusion and none of the exclusion criteria to qualify for participation in Study AMAH.

If, at LVTP of the originating study, a patient is not able to enter Study AMAH (for example, due to unresolved safety concerns), the patient will be evaluated in the originating study for up to 12 weeks beyond the LVTP (that is, in a post-treatment follow up period) to determine whether treatment with investigational product can resume in Study AMAH. If, in the opinion of the investigator, starting or restarting treatment with mirikizumab does not pose an unacceptable risk, the patient can begin participation in Study AMAH, that is, have Visit 1 in Study AMAH. Eligible patients must enter Study AMAH within 12 weeks of the LVTP of originating study or they will become ineligible.

[Figure AMAH.5.1](#) illustrates the study design.

Abbreviations: LV = last study visit; miri = mirikizumab given as subcutaneous injection (SC); PRN=as needed; pts = patients; Q8W =every 8 weeks; V = visit; W or w = week.

^aPatients will remain blinded to treatment until the last patient completes the last originator study.

^bPatients receiving 125 mg Q8W may be eligible to escalate to 250 mg Q8W;

Figure AMAH.5.1. Illustration of study design for Clinical Protocol I6T-MC-AMAH.

Screening: There will be no screening period for Study AMAH. Visit 1 (Week 0) of Study AMAH may occur at the last visit, and within 12 weeks after the last visit, of the originator study.

Treatment Period: All patients participating in Study AMAH will receive mirikizumab Q8W SC. The dose used in Study AMAH will depend on the treatment patients were receiving during the qualifying period of the originator study. For all treatment groups in Study AMAH, dosing begins at Visit 1 (Week 0) and continues to Visit 21 (Week 208).

- Patients entering from Study AMAJ or Study AMAK who received mirikizumab during the qualifying period, will continue to receive the dose they were receiving (either 250 mg mirikizumab Q8W SC or 125 mg mirikizumab Q8W SC). Patients entering from Study AMAJ or Study AMAK who were receiving secukinumab or placebo, respectively, during the qualifying period will receive 250 mg mirikizumab Q8W SC.
- Patients entering from Study AMBK will receive 250 mg mirikizumab Q8W SC.
- Patients entering from Study AMAF whose last treatment was 300 mg mirikizumab Q8W, on either the fixed dosing regimen or in the as needed (PRN) regimen, will start 250 mg mirikizumab Q8W SC in Study AMAH. Patients entering from Study AMAF whose last treatment was either 30 mg or 100 mg mirikizumab on a PRN regimen will start 125 mg mirikizumab Q8W SC in Study AMAH.
- After Study AMAH dosing is no longer blinded, patients who in the opinion of the investigator have experienced significant clinically meaningful loss of efficacy during study participation may be increased from 125 mg mirikizumab Q8W to 250 mg mirikizumab Q8W if it is determined by the patient and the investigator that the patient

might benefit from additional study drug in order to achieve satisfactory disease control. All patients who increase dosing to 250 mg mirikizumab Q8W will remain on this dose until completion of the study or early discontinuation.

Post-Treatment Follow-Up Period (12 Weeks): All patients, whether they discontinue early for any reason or complete study treatment, will enter the 12-week Post-Treatment Follow-Up period (Visit 801 and Visit 802) of Study AMAH.

For patients who have entered the Post-Treatment Follow-Up Period, psoriasis therapy with another agent(s), as determined appropriate by the investigator, is allowed.

5.2. Determination of Sample Size

The sample size for Study AMAH will be determined by the number of patients who enroll in Study AMAH from the originator studies. Approximate planned sample sizes for Studies AMAF, AMAJ, AMAK, and AMBK are respectively 205, 1440, 500, and 300. Based on the assumption that 80% to 90% of patients complete the originator studies and 80% to 90% of the completers continue on into Study AMAH, Lilly anticipates that approximately 1600 to 2000 patients will enter Study AMAH.

5.3. Method of Assignment to Treatment

All patients participating in Study AMAH will receive mirikizumab Q8W SC. The dose used in Study AMAH will depend on the treatment patients were receiving during the qualifying period of the originator study.

6. A Priori Statistical Methods

6.1. General Considerations

Statistical analysis of this study will be the responsibility of Eli Lilly and Company (hereafter, Lilly) or its designee. The latest version of the Medical Dictionary for Regulatory Activities (MedDRA[®]) will be used.

Analyses and summaries from assessment of endpoints described in [Table AMAH.4.1](#) of this Statistical Analysis Plan are planned to be included in the clinical study report (CSR). Analyses and summaries for key safety data are also planned to be included in the CSR. Results from additional efficacy analysis pre-defined below and other safety analyses may also be provided in the CSR, as deemed appropriate. Any analysis or summary not included in the CSR will be available upon request.

Any change to the data analysis methods described in the protocol will require a protocol amendment ONLY if it changes a principal feature of the protocol. Any other change to the data analysis methods described in the protocol and the justification for making the change will be described in the CSR.

Additional exploratory analyses of the data may be conducted, as deemed appropriate. Some of these additional supplementary analyses will be prespecified in a separate supplemental SAP.

Some of the analyses described in this document will be incorporated into interactive display tools instead of or in addition to static displays.

The Schedule of Activities outlined in the protocol specifies the allowable windows for assessments. Assessments performed outside these windows will not be excluded from any analysis.

